born to mothers with opportunity to receive HPV vaccination prior to delivery; birth cohorts 2008 to 2020) is approximately 100, 50, and 50, respectively (total=200). Study power was estimated according to varying number of cases (100 to 300) and effect size (odds ratio from 3 to 4) and overall female vaccination exposure rate (5% to 10%) in the maternal birth cohorts of interest, with constant alpha-level of 0.05, and control/case ratio of 10 or 100 [Table 1]. With 200 cases originating from 2008-2020 birth cohorts, the estimated power assuming true odds ratio of 3.0 is 92% (10 controls per case) and 94% (100 controls per case). Precision was also taken into account by specifying that the analyses for the primary objective be powered to detect an odds ratio of at least 3.0, with a lower bound for the confidence interval of at least 1.33, which is equivalent to lower bound of 95% confidence interval of vaccine effectiveness  $\geq 25\%$ . This level of precision is attainable within the study power calculation assuming  $\geq 120$  incident JoRRP cases are observed (with 100 controls per case) or  $\geq 140$  incident JoRRP cases are observed (with 10 controls per case) in the cohort of interest. Herd protection was not considered in evaluation of study power for two reasons: 1) In the Nordic region, the average maternal age at birth of first child is ~29 years and in older birth cohorts vaccination rates are much lower, and 2) Males, who are typically the vectors of infection, were not targeted for vaccination until very recently. To examine the potential effect of herd protection and test this assumption, age-standardized incidence rates of JoRRP will be calculated according to maternal vaccination status to assess changes in incidence in pre- and post-vaccination periods among children of unvaccinated mothers, e.g., through calculation of annual percent change.

It is important to note that these approximate counts were generated for the purpose of power estimation only through accessing publicly available gross statistics on ICD codes for otorhinolaryngological diseases, and that no preliminary analyses evaluating the association between HPV vaccination and RRP have been performed.

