OR=3	5%	0.68	0.76	0.82	0.87	0.92	0.93	0.96	0.98
	10%	0.86	0.93	0.92	0.98	0.99	0.99	1	1
OR=3.5	5%	0.83	0.90	0.93	0.96	0.98	0.99	0.99	1
	10%	0.96	0.99	0.99	1	1	1	1	1
OR=4	5%	0.92	0.96	0.98	0.99	1	1	1	1
	10%	0.99	1	1	1	1	1	1	1
Control/case ratio of 100									
OR=3	5%	0.72	0.80	0.86	0.91	0.94	0.96	0.97	0.98
	10%	0.90	0.95	0.98	0.99	0.99	1	1	1
OR=3.5	5%	0.86	0.92	0.96	0.97	0.99	0.99	1	1
	10%	0.98	0.99	1	1	1	1	1	1
OR=4	5%	0.95	0.98	0.99	1	1	1	1	1
	10%	0.99	1	1	1	1	1	1	1

**Note:** For OR=3 and 5% vaccination coverage, >80% power would be achieved with 140 cases with 10 controls per case and 120 cases with 100 controls per case.

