## 12 ANNEXES

### Annex 1 OVERVIEW OF POTENTIAL CONFOUNDING IN ASSESSMENT OF HPV VACCINE EFFECTIVENESS AGAINST JUVENILE-ONSET RRP

#### **Definitions:**

[figure not shown]
Study exposure: Maternal HPV vaccination with GARDASIL or GARDASIL 9, below called HPV vaccination.

Study outcome: Juvenile-onset recurrent respiratory papillomatosis.

Primary objective: Estimate odds ratio (OR) of JoRRP (yes/no) given HPV vaccination in biologic mother (yes/no).

Power: The study has >80% power to detect an OR of 3.0 with a lower bound of the 95% confidence interval of >1.33, assuming at least 120 cases of JoRRP are observed.

Main association of interest:

The hypothesis is that maternal HPV vaccination is negatively associated with the odds (likelihood) of JoRRP. Factors that may act as confounders to this association are considered, below. That is, factors associated with both exposure and outcome in such a way that an observed association between the two is partially or completely confounded. Given that causal HPV infections in cases of JoRRP are acquired vertically (from mother-to-child during delivery), many of the same factors considered here as confounders in evaluating the association between HPV vaccination and JoRRP are the same as those considered in evaluating the association between HPV vaccination and AoRRP.

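### Power above 80% at 120 cases with 100 controls per case does not fit Table 1, whose own row puts it at about 78–79%

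*Protocol*

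**What the plan says.** Section 7.5 plans on about 200 cases and sets out power in Table 1 "with constant alpha-level of 0.05, and control/case ratio of 10 or 100", for an "overall female vaccination exposure rate (5% to 10%) in the maternal birth cohorts of interest". Success in these calculations means an odds ratio estimated "with a lower bound for the confidence interval of at least 1.33". At 200 cases, "the estimated power assuming true odds ratio of 3.0 is 92% (10 controls per case) and 94% (100 controls per case").

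Three places then give a smaller reference count:

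- **Note to Table 1**, for an odds ratio of 3 and 5% coverage: ">80% power would be achieved with 140 cases with 10 controls per case and 120 cases with 100 controls per case".
- **Section 7.5 text**: "This level of precision is attainable within the study power calculation assuming" at least 120 cases (100 controls per case) or at least 140 (10 controls per case). This sentence gives no power percentage.
- **Annex 1, Definitions (Power)**: power above 80%, "assuming at least 120 cases of JoRRP are observed". No control ratio is given.

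The Table 1 row for 100:1, odds ratio 3 and 5% coverage begins "0.72 0.80 0.86" at 100, 125 and 150 cases. The corresponding 10:1 row gives 0.68, 0.76 and 0.82.

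**The concern.** The note summarises the table directly above it, and at 100:1 the two disagree. If power is 0.80 at 125 cases, it cannot be above 0.80 at 120. Annex 1 repeats the 120 without the ratio. Controls are sampled at up to 100 per case and Table 1 also covers 10:1, so a reader of Annex 1 alone cannot tell which row applies.

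The stake is modest. Once the registries deliver, somebody will ask whether the number of cases is enough. The 120 and 140 are the only small reference counts in the protocol that are tied to a power level, so they should agree with the table behind them.

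**Working it through.** **Inputs (section 7.5 and Table 1).** True odds ratio 3.0; exposure 5% in controls; success if the lower limit of the two-sided 95% confidence interval exceeds 1.33; 100 or 10 controls per case.

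**Step 1: read the table.** Linear interpolation at 100:1 and 120 cases:

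0.72 + (120 − 100)/(125 − 100) × (0.80 − 0.72) = 0.72 + 0.8 × 0.08 = **0.784**.

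Interpolating on the probit scale against the square root of the case count gives 0.786, or 0.781 to 0.791 allowing for two-decimal rounding.

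**Step 2: can rounding rescue the note?** In this range power rises with the number of cases at a decreasing rate. Power at 120 therefore lies on or below the line through the 125 and 150 entries extended back to 120:

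power(120) ≤ 1.2 × power(125) − 0.2 × power(150).

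Taking the rounding most favourable to the note (0.805 at 125 and 0.855 at 150): 1.2 × 0.805 − 0.2 × 0.855 = 0.966 − 0.171 = **0.795**. That is still below 0.80.

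**Step 3: reproduce the table, then compute at 120.** Exposure among cases is 3 × 0.05/(1 + 2 × 0.05) = 0.1364. Two calculations were run: exact enumeration of independent binomial counts with a Wald interval for the log odds ratio, and simulation of matched sets analysed by conditional logistic regression (40,000 replicates at the key counts).

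| Ratio | Cases | Table 1 | Enumeration | Simulation, Wald / score |
|---|---|---|---|---|
| 100:1 | 120 | – | **0.787** | **0.789 / 0.795** |
| 100:1 | 125 | 0.80 | 0.804 | 0.804 / 0.809 |
| 100:1 | 150 | 0.86 | 0.862 | 0.858 / 0.862 |
| 10:1 | 125 | 0.76 | 0.757 | 0.749 / 0.757 |
| 10:1 | 140 | – | 0.792 | 0.795 / 0.802 |
| 10:1 | 150 | 0.82 | 0.818 | 0.815 / 0.820 |

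At 100:1 the enumeration also gives 0.723 at 100 cases (table 0.72) and 0.934 at 200 (table 0.94). The row is reproduced closely enough to use for 120.

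**Step 4: where 80% is passed at 100:1.** Enumeration gives 0.797 at 123 and 0.801 at 124. Simulation gives 0.7996 (Wald) or 0.8044 (score) at 123. Probit interpolation of the table first exceeds 0.80 at 126. About 125 is a fair single figure.

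**Step 5: the 10:1 figure.** Linear interpolation at 140: 0.76 + (15/25) × 0.06 = 0.796. Rounding of the two entries allows 0.4 × 0.755 + 0.6 × 0.815 = 0.791 up to 0.4 × 0.765 + 0.6 × 0.825 = 0.801. Simulation gives 0.795 to 0.802. The table does not contradict the 140.

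**Step 6: Annex 1 without a ratio.** On the 10:1 row, 120 cases give 0.68 + 0.8 × 0.08 = 0.744.

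**The case against.** **The gap is too small to matter.** It is about 0.5 to 2 points, or a handful of cases, against about 200 planned, where stated power is 92–94%. Table 1 is not exact to the point either: its 10:1 row for an odds ratio of 3 and 10% coverage falls from 0.93 at 125 cases to 0.92 at 150. This stands as to size, and is why the point is minor. It does not make the note agree with its own row.

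**Both counts are wrong.** A reader might infer that 140 at 10:1 is also contradicted. It is not: the table has no 140 column, and the interpolated range includes 80%.

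**The threshold for going ahead is too low.** A reader might infer that 120 or 140 cases would let the analysis proceed under-powered. The documents do not support that. Section 7.5 fixes no such count. Power is to be calculated on the actual number of cases, before any analysis and without knowledge of the vaccination status of the cases' mothers, and the analysis is deferred if power is insufficient. The section 7.5 sentence with the two counts calls the precision attainable and gives no 80% figure.

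**The figure depends on Table 1's model.** This stands. Table 1 is reproduced when exposure raises the odds threefold (13.6% exposed among cases), whereas the hypothesis is a protective effect. That is a separate and larger question about the table, which correcting 120 to 125 does not address.

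**Conclusion.** Within Table 1's own model, the claim of more than 80% power at 120 cases with 100 controls per case is wrong by a small margin. Power there is about 78–79% (78.4% by linear interpolation; 78.7% to 79.5% recomputed). About four to six more cases are needed to pass 80%. The error appears in the note to Table 1 and in Annex 1, and the same count is carried in the section 7.5 text. Annex 1 has the further defect of omitting the ratio on which the count depends. The 10:1 count of 140 can stand as about 80%.

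The conclusion rests on a true odds ratio of 3, 5% exposure in controls, a lower confidence limit above 1.33, and power that rises smoothly with the number of cases. It is a minor correction of a stated figure, with no consequence for the rule on whether to proceed.

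**What to change.** - **Note to Table 1 and section 7.5 text:** replace 120 with about 125 cases at 100 controls per case, described as about 80% power because the table reads 0.80 there. Alternatively, keep 120 and say about 79%.
- **Annex 1, Power:** make the same change and state that it assumes 100 controls per case.
- **The 140-case figure at 10:1:** no change is required. If the note is being edited, about 80% is the safer wording.
- If Table 1 is recomputed for another reason, including the direction of the effect, take all of these counts from the new table.

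The cost is three short wording changes, with no effect on design, data or analysis.

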## 7.6 Data Management

Prior to initiating this study, a common data model will be prepared along with transfer agreement for Denmark to receive data from Sweden and Norway, including preparation of a clear management plan for data handling to ensure protection of subject privacy. The data management of the variables will be performed before sending the final data to Denmark.

All data collected for the study should be recorded accurately, promptly, and legibly. For primary data collection, the investigator or qualified designee is responsible for recording and verifying the accuracy of subject data. For data *not* obtained from a primary source (i.e., secondary data, such as claims and electronic health records), the investigator is responsible for reviewing data quality and relevance to the best of the investigator's knowledge. By signing this protocol either electronically or written, the investigator confirms that the quality and relevance of data has been assessed to meet the minimum requirements for all study objectives.

PRODUCT: V501/V503	PROTOCOL/AMENDMENT VERSION NO.: V503-095-00-v3
REVOPS ID NO: NIS102781	CORE DRC APPROVAL DATE: 18MAR2024
EPIDEMIOLOGY NO.(PE STUDIES ONLY): 08039.022	

If this study has been outsourced, the institutional policies of the supplier should be followed for development of data management plans. However, the supplier should ensure compliance with Good Pharmacoepidemiology Practice, and all applicable federal, state, and local laws, rules and regulations relating to the conduct of the study.

### **Data Management Software and Hardware (per country):**

#### *Sweden*

- SAS version 9.4 will be used for data management and statistical analyses.
- Stata version 18.0 will be used for statistical analyses.
- R may be used for complimentary statistical analyses and generation of graphs.
- All hardware utilized in the study is procured through central KI purchasing procedures and follow strict regulations on performance and capacity.

#### *Norway*

- All data management and statistical computing on registry data delivered to the project will be performed in the most recent version of Stata (currently 18.0 MP (StataCorp) or R, using syntax scripts generated by the CRN study team. All syntax that influences the dataset (data management) or generates results (analyses) is stored in the project data script folder on CRN's secure server. Syntax files will be numbered according to the order in which they should be run. All syntax written by one member of the CRN study team is checked by another member of the CRN study team. All output (results) is also assessed by the CRN study team, and any unexpected result is investigated further to double-check that no scripting error has occurred. Tables and figures are transferred to the report template by one member of the CRN study team and the transfer is checked by another member of the CRN study team. All data management, analyses or other data procedures are logged, including information on when the procedure took place and who performed the procedure.

#### *Denmark*

- A data management plan will be developed to guide and instruct the data manager on the project. This will include a list of the registers used (see section 7.4) and a detailed instruction on the criteria for data extraction from each register. Furthermore, the steps listed in section 7.7 will be part of the data management plan. All steps in data management plan will be gone through between the data manager and investigator before execution and evaluated after execution. The SAS software and the R statistical software will be used in the data management.

PRODUCT: V501/V503	PROTOCOL/AMENDMENT VERSION NO.: V503-095-00-v3
REVOPS ID NO: NIS102781	CORE DRC APPROVAL DATE: 18MAR2024
EPIDEMIOLOGY NO.(PE STUDIES ONLY): 08039.022	

## Description of Data Preparation and Methods for Data Retrieval and Collection (per country):

### *Sweden*

- All data retrieval is documented and traceable through the formal data specification orders exchanged with the registry data holders before data delivery, inclusive of exact variable and format lists.
- Data collection will take place from Swedish registry data holders through the import of SAS.7bdat format and/or CSV files. Only electronic data will be used, there are no paper-based data in this project. No eCRFs are applicable.
- Data quality checking will occur right after delivery from the registry data holder, ensuring that requested data are logical and transparent. Data cleaning will be done using SAS version 9.4 and documented through log files and validation procedures as described below.

### *Norway*

- Data collection will take place from Norwegian registry data holders through the import of CSV and/or data files. Each registry will securely transfer data to the delivery unit at the CRN, including:
  - RRP incidence data from the Norwegian Patient Registry (NPR)
  - HPV vaccination status from the Norwegian Immunisation Registry (SYSVAK)
  - Prescription data from the Norwegian Prescribed Drug Registry
  - Sociodemographic data from Statistics Norway
  - Norpat codes from the Norwegian Cancer Registry (CRN)
  - Population data from the National Population Registry

Only electronic data will be used, there are no paper-based data in this project. Data received from each registry will be documented by a data-in procedure, including quality checks of incoming data and documentation of data reception and links to the application for data, the data file itself and any documentation accompanying the data file. Data-in and its associated forms are stored in the project data documentation folder. General quality checks of incoming data are carried out to ensure that the data delivery coincides with the data application, e.g., that all the expected variables have been included and contain the expected information, and that the correct number of individuals have been included. Checks should be carried out and any errors reported

PRODUCT: V501/V503	PROTOCOL/AMENDMENT VERSION NO.: V503-095-00-v3
REVOPS ID NO: NIS102781	CORE DRC APPROVAL DATE: 18MAR2024
EPIDEMIOLOGY NO.(PE STUDIES ONLY): 08039.022	

to the delivering registry within 2 weeks of receipt of data. Any new deliveries of data will be documented by the data-in procedure. All raw data received from the registries will be stored on CRN's secure server as they were delivered to the project, with access restricted to project members only. All data and associated files are backed up regularly and automatically. Data cleaning will be done using Stata or R and documented through syntax scripts and validation procedures as described above.

### ***Denmark***

- All data collected in this project are electronic data derived from existing registers (section 7.4). Data will be collected according to the specified criteria in the data management plan i.e., specified age intervals, specified diagnoses etc.
- A data management plan will be developed for this protocol.
- No data collector is used in this protocol.

### **7.7 Programming Quality**

Good programming standards should be followed during all programming associated with the study. No error statements should occur when programs are run. Warning statements should be avoided whenever possible. If warning statements do appear, they should be accompanied by explanatory text, stating why they do not represent a program. A Programming Information Document should be drafted that describes:

- the order by which the SAS or other software programs were run;
- a description of the SAS or other software programs;
- the program's name, location, and author;
- the date of creation and modification where applicable;
- the name and location of the SAS or other software datasets input and output; and
- the purpose of the program.

Data validation should occur throughout the data management and analysis process. Data quality checks may include, but are not limited to, programming checks by an individual who is not main programmer for the study, internal dataset consistency, consistency between datasets, external checks with other available databases for verification of items such as birthdates and vaccination dates and checks to ensure that protocol and SAP criteria were met. If validation checks were not satisfied, then an examination of the problem should be performed on the dataset or datasets in question and the problem resolved. All data validation, quality checks, and resolution of issues identified should be recorded on a standardized form used for this study.

PRODUCT: V501/V503	PROTOCOL/AMENDMENT VERSION NO.: V503-095-00-v3
REVOPS ID NO: NIS102781	CORE DRC APPROVAL DATE: 18MAR2024
EPIDEMIOLOGY NO.(PE STUDIES ONLY): 08039.022	

Institution will retain copies of electronic versions of the analytic datasets and programs, and computer printouts. This includes any relevant computer code that produces the basis of tables, discussions, graphs, or interpretations in the study report.

The procedures are applicable to all study programing, tables and figures associated with study final report, and additional analyses requested by MSD.

## 7.8 Data Analysis

### 7.8.1 Statistical Methods

Conditional logistic regression will be used for estimation of odds ratios (ORs) and corresponding 95% confidence intervals in the pooled analysis using 1-step approach, with adjustment for clustering and adjustment for relevant covariates; all measured with similar high accuracy in each country. Children whose mother received the bivalent vaccine, even in combination with GARDASIL or GARDASIL 9, will be excluded from the analysis. Similarly, in the primary analysis, children whose mother had history of genital warts prior to vaccination will be excluded as vaccination is exclusively prophylactic, i.e., there is no therapeutic effect against HPV infection or related disease.

Each case subject and his/her controls constitute a risk stratum, or a risk set matched on age of mother, sex of child, and region where case was diagnosed. The distribution of these factors is therefore equalized in the model by design, which removes the need for adjusting for these factors so long as the risk strata are retained. Regarding mode of delivery, history of maternal genital warts, maternal smoking status, education level and income, it was decided not to match on these factors, as they may be of interest to study as confounders or effect modifiers.

When the outcome of a study is rare, which is the case for JoRRP, the OR approximates the risk ratio (or relative risk, RR) [35]. Further, incidence density sampling (i.e. random sampling of controls from the available population still at-risk at the particular point in time of the case's diagnosis) also ensures that ORs are a direct estimate of the hazard ratio, again interpretable as the risk ratio in our study [36]. ORs obtained through the conditional logistic regression model will therefore be interpreted as the corresponding RR.

It is expected that use of ICD-10 code D14.1 will be highly accurate for diagnosis of RRP; however, where possible, effort will be made to further increase specificity, applying appropriate topography/morphology codes. We also plan to perform sensitivity analyses restricted to RRP cases with related diagnostic or other treatment procedures, and/or subcode D14.1.A, as described above.

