Given the high attribution of targeted HPV types 6 and 11, high GARDASIL (recombinant HPV quadrivalent [types 6, 11, 16 and 18] vaccine) and GARDASIL 9 (recombinant HPV nonavalent [types 6, 11, 16, 18, 31, 33, 45, 52 and 58] vaccine) vaccine effectiveness is expected against RRP. A recent Australian surveillance study found that the incidence rate of JoRRP declined from 0.16 per 100,000 in 2012 to 0.02 per 100,000 in 2016 ( $p=0.03$ ) following introduction of an extensive GARDASIL vaccination program [12]. This program initially targeted females 12-26 years in 2007-2009, and achieved very high coverage, e.g., >85% of girls <16 years of age received at least one dose. Among 15 incident JoRRP cases observed in this study, none of the mothers of these cases received vaccination prior to pregnancy, and 20% had a maternal history of external genital warts. Further, 13/15 of the affected children were born vaginally, and all genotyped cases ( $n=7$ ) were either HPV6 ( $n=4$ ) or HPV11 ( $n=3$ ) positive [12]. Similarly, investigators recently reported a significant decline in the incidence of JoRRP following HPV vaccine introduction in the United States, from 2 per 100,000 births (in 2004-2005 birth cohort) to 0.5 per 100,000 births (in 2012-2013 birth cohort), which the authors suggest is most likely due to GARDASIL vaccination [11].

In evaluating the impact/effectiveness of GARDASIL against JoRRP it is important to consider the unique mechanism of acquisition of causal HPV infections, i.e., mother to child transmission during delivery. To observe an effect, the vaccinated female must become pregnant and deliver a child with sufficient opportunity to develop JoRRP, considering also that the peak age of JoRRP onset is between 2 to 4 years. The earliest cohort of girls vaccinated in school-based programs (10-13 years of age) in 2007 would reach a maximum age of 23-26 years (1992-1995 birth cohorts) in 2020, with few cases of JoRRP expected to be diagnosed among children born to mothers from these birth cohorts at this point in time. But considering the rapid decline in JoRRP already observed in the United States and in

PRODUCT: V501/V503	PROTOCOL/AMENDMENT VERSION NO.: V503-095-00-v3
REVOPS ID NO: NIS102781	CORE DRC APPROVAL DATE: 18MAR2024
EPIDEMIOLOGY NO.(PE STUDIES ONLY): 08039.022	

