Potential confounders such as mode of delivery, as well highest level of family income and education achieved by the mother (tentatively in tertiles relative to the general age-matched population in each of the respective countries) will be adjusted for when investigating the primary objective, through inclusion in the conditional logistic regression. Sensitivity analyses will be conducted in relation to the primary objective to assess the impact of: vaccine exposure definition (fully vaccinated versus  $\geq 1$  vaccine dose), age at vaccination ( $< 17$  years versus  $\geq 17$  years), outcome definition (ICD-10 code D14.1 versus cases [of D14.1] that have at least one associated treatment/procedural code and/or specified with subcode D14.1.A/“larynx papilloma”), time since vaccination ( $\leq 10$  years versus  $> 10$  years), and maternal history of EGW prior to delivery (yes versus no). To assess if older vaccinated women are a higher risk group, history of genital warts will also be presented separately among vaccinated women (i.e., history of genital warts prior to vaccination), stratified according to attained age at time of vaccination and compared with history of genital warts among unvaccinated women with same attained age. In the analysis, the group of women with history of genital warts prior to vaccination will be considered separately, if appropriate, i.e., assuming history of genital warts is not strongly associated with HPV vaccine uptake. If vaccination is found to be effective in preventing JoRRP among children whose mother had history of EGWs prior to delivery then it would suggest that vaccination not only prevents acquisition of infection in the mother but also prevents transfer of infection from infected mother to child, e.g., through maternal transfer of antibodies or other mechanism. OR estimates from the regression model will be inspected in terms of point estimates and precision, for comparison with results from the main analysis. Effect size (OR) estimates are expected to vary across most sensitivity analyses. For example, effectiveness may be higher among females that are fully vaccinated, vaccinated at younger age (prior to sexual debut), and without history of EGW.

There will be no adjustment for multiple comparisons in this study. Analyses have been pre-specified, discriminating between primary and sensitivity analyses, and all results will be reported.

PRODUCT: V501/V503	PROTOCOL/AMENDMENT VERSION NO.: V503-095-00-v3

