#### 4. Maternal history of genital warts

The lead risk factor for JoRRP is a maternal history of genital warts. Most children who develop RRP are born to mothers with genital warts [55]. In the same Danish retrospective cohort study cited above, children born to mothers with history of genital warts were found to have ~230-fold increased risk of JoRRP compared to children born to mothers without history of genital warts (RR=231.4, 95% CI=135.3-395.9) [4]. Investigators also reported that longer delivery ( $\geq 10$  hours versus  $< 10$  hours) was associated with a two-fold greater risk of JoRRP (RR=2.0, 95% CI=1.1-3.5), which suggests vertical transmission of HPV infection during delivery [4].

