 A mother who received 3 doses (or 2 doses administered at 0 and 6-12 months if <15 years of age) of GARDASIL or GARDASIL 9 one year prior to delivery, without history of genital warts prior to vaccination, will be classified as exposed.

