### Notes on Table 3:

1. In countries where topography/morphology codes cannot be obtained from pathology or cancer registry, separate tables will be prepared with outcome defined using: a) subcode D14.1.A, and b) code D14.1 and/or subcode D14.1A with at least one appropriate procedural code, i.e. DQB10 (Endoscopic extirpation), UDQ25 (Microlaryngoscopy with biopsy), and/or UDQ22 (Microlaryngoscopy).
2. Separate tables will be prepared: a) considering age at vaccination (<17 years vs. ≥17 years), b) considering time since vaccination of mother (≤10 years vs >10 years), c) considering maternal history of genital warts prior to delivery (yes/no), and d) irrespective of maternal history of genital warts prior to delivery/vaccination. In the event that there are <5 counts in an individual cell of any stratified table, it will not be possible to include exact counts due to strict data protection regulation in Europe.
3. Separate tables will be prepared with exposure defined as receiving at least one dose of GARDASIL/GARDASIL 9 vaccine.
4. Separate tables will be prepared focusing on GARDASIL use only as exposure.

PRODUCT: V501/V503	PROTOCOL/AMENDMENT VERSION NO.: V503-095-00-v3
REVOPS ID NO: NIS102781	CORE DRC APPROVAL DATE: 18MAR2024
EPIDEMIOLOGY NO.(PE STUDIES ONLY): 08039.022	

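### The primary-analysis exclusion for genital warts before vaccination can act only on vaccinated mothers, so it biases the primary odds ratio in the vaccine's favour by an amount the protocol does not allow one to fix

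*Protocol*

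**What the plan says.** Section 7.8.1 (Statistical Methods) sets the rule: "in the primary analysis, children whose mother had history of genital warts prior to vaccination will be excluded as vaccination is exclusively prophylactic". Table 3 footnote 4 in Annex 2 builds the same condition into the definition of the fully vaccinated row, where a mother "without history of genital warts prior to vaccination, will be classified as exposed". No matching condition is set for the unvaccinated row.

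Section 7.8.2 describes the same women less firmly: "the group of women with history of genital warts prior to vaccination will be considered separately, if appropriate", on the assumption that warts history is not strongly associated with uptake.

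Annex 1 calls maternal warts the lead risk factor and reports, from a Danish retrospective cohort, "RR=231.4, 95% CI=135.3-395.9". It adds: "Most children who develop RRP are born to mothers with genital warts". The Background gives a lower figure from an Australian series of 15 cases, in which "20% had a maternal history of external genital warts".

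Warts history is deliberately not matched on (7.8.1). Section 7.2.3 names adjustment as one option among several, but Table 3 footnote 3 leaves warts off its list of adjustment factors and Annex 1 says adjusting may be inappropriate. Outside the primary analysis, the plan has tables by warts history before delivery and one "irrespective of maternal history of genital warts prior to delivery/vaccination" (Notes on Table 3, note 2).

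**The concern.** The stated reason for the exclusion is that vaccination cannot treat an existing infection. That reason supports comparing vaccinated and unvaccinated mothers who were both free of warts at the time when vaccination happened or could have happened. The rule as written does something else. It is tied to a date that only vaccinated mothers have, so unvaccinated mothers who had warts at the same age stay in the comparator with their high-risk children.

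Success is judged on the primary odds ratio (section 7.5: at least 3.0, with a lower 95% bound of at least 1.33). An exclusion that lowers baseline risk on one side only raises that ratio even if the vaccine does nothing. Annex 1 tells the reader to expect confounding by sexual behaviour to run toward the null; this exclusion runs the other way and is not declared as a source of bias.

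**Working it through.** **The plan's own figure.** The protocol states no size for this bias. Its nearest figure is power at 200 cases, 5% coverage and an odds ratio of 3.0: 94% with 100 controls per case and 92% with 10. Simulating an unmatched table with a Wald 95% interval (200,000 runs, lower bound above 1.33) gives 93.5% and 90.5%. At 100 cases it gives 72.4% and 66.3%, against 0.72 and 0.68 in Table 1. The figures reproduce within 2 points when the 5% group is given the threefold higher odds; whether that is the right orientation is a separate question.

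**Who can be excluded.** A never-vaccinated mother cannot be. A mother first vaccinated after delivery could literally be caught by 7.8.1 although unexposed at delivery. Vaccinated mothers whose warts appeared after vaccination stay in.

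**Expected odds ratio with no vaccine effect.** Let p be the share of mothers with warts by delivery, s the share of those warts arising before vaccination, and R the risk ratio for warts, with p equal in both groups before exclusion.

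- Relative risk in unvaccinated mothers: 1 + (R−1)p.
- Warts prevalence left in vaccinated mothers after exclusion: pv = p(1−s)/(1−ps).
- False odds ratio: [1 + (R−1)p] / [1 + (R−1)pv].
- Writing f = pR/[1 + (R−1)p] for the share of unvaccinated cases with maternal warts, this simplifies to (1−ps)/(1−fs).

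The documents give R (231.4) and two anchors for f (20%, and more than half). They give neither p nor s for this population; those are assumptions.

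Example, f=20%, p=1%, s=50%: (1−0.005)/(1−0.10) = 0.995/0.90 = 1.11.

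| Setting | s=25% | s=50% | s=75% | s=100% |
|---|---|---|---|---|
| f=20%, p=1% | 1.05 | 1.11 | 1.17 | 1.24 |
| f=50%, p=1% | 1.14 | 1.33 | 1.59 | 1.98 |
| R=231.4, p=1% (f=2.314/3.304=70%) | 1.21 | 1.53 | 2.09 | 3.30 |
| R=20, p=5% (f=1/1.95=51%) | 1.13 | 1.31 | 1.56 | 1.95 |

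The R=20 row is included because the reference list titles the Danish study as one of condyloma in pregnancy, whereas warts before vaccination here precede a course completed at least a year before delivery. The risk ratio for warts that old may be lower.

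**Chance of meeting the success rule with no effect** (simulated; 200 cases, 100 controls per case, R=231.4, p=1%):

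| Coverage | s=50% | s=90% |
|---|---|---|
| 5% | 1% | 11% |
| 10% | 3% | 42% |

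With no exclusion, or a symmetric one, the expected odds ratio is 1.00 and the chance is about 0.1% or less.

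**The case against.** The strongest reply is that the plan already contains the means to see the problem. Section 7.8.2 compares warts before vaccination with warts in unvaccinated women of the same attained age. Note 2 to Table 3 adds tables by warts history before delivery, whose no-warts stratum restricts both groups alike, and a table that ignores warts history. Results are also split at age 17 at vaccination, and all will be reported. This stands as far as disclosure goes. It does not correct the primary estimate, on which success is judged.

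A second reply also stands in part. If prior warts raise uptake, as Annex 1 allows, having no exclusion would bias toward the null. The one-sided rule does not balance that; it replaces one bias with another in the opposite direction.

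Four stronger readings are tempting but not supported:

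- A reader might apply the 231-fold risk to every excluded mother and conclude that a warts prevalence of 0.87% alone takes a null vaccine to the 3.0 threshold (1 + 0.0087 × 230.4 = 3.0). That assumes no warts arise between vaccination and delivery, and implies that 0.0087 × 231.4 / 3.0 = 67% of unvaccinated cases have maternal warts from before the vaccination age. It is an upper bound.
- A reader might infer from footnote 4 that vaccinated mothers with prior warts move to the unexposed row. Section 7.8.1 says they are excluded, and the comparator row is labelled unvaccinated.
- A reader might take the Background remark about catch-up ages as describing these mothers. It concerns the United States and Australia. For this study, section 7.3.1 says only that few cases come from mothers born in 1992 or later, which makes vaccination at older ages plausible but gives no wart prevalence.
- A reader might call sections 7.8.1 and 7.8.2 flatly contradictory. Separate consideration can mean exclusion from the primary analysis plus separate presentation. The wording is loose, and its condition (if appropriate) leaves the primary population open.

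**Conclusion.** The point holds. The exclusion acts on one exposure group, concerns the strongest risk factor the protocol names, and is not offset by matching or by the listed adjustment factors. Its own contribution to the primary odds ratio is always in the vaccine's favour whenever some warts precede vaccination and warts raise risk.

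The size is unknown from the documents. On the protocol's two anchors for the share of cases with maternal warts, with p=1%, it ranges from 1.05 to 1.98. It reaches 3.30 only at R=231.4 with every wart preceding vaccination. All figures assume equal warts prevalence in the two groups before exclusion. The documents therefore support saying that the primary estimate is biased, but not that the bias alone would deliver a successful result. Because the rule defines the primary population, it should be corrected before the analysis is run.

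**What to change.** Apply the exclusion to both groups. Give each unvaccinated mother a reference date, for example the vaccination date or age drawn from vaccinated mothers of the same birth year and country, and exclude any mother, vaccinated or not, with warts recorded before her date. The same-attained-age comparison in section 7.8.2 already uses this logic, and the registry data are already requested.

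Keep the table that ignores warts history (note 2(d)) as a prominent sensitivity analysis. If it is made primary instead, state the expected bias toward the null from higher uptake after warts. Reword 7.8.1, 7.8.2 and footnote 4 so that they define one primary population.

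The cost is protocol wording, one programming step, a smaller odds ratio and fewer cases. The symmetric rule drops roughly f × s of the unvaccinated cases. Treating nearly all of the expected 200 as unvaccinated, the loss is at most about 200 × 0.20 = 40 at f=20% and 200 × 0.50 = 100 at f=50% (both with s=100%). The second would leave 100, below the 120 cases that section 7.5 requires for 80% power with 100 controls per case; Table 1 gives 0.72 at 100 cases for an odds ratio of 3 and 5% coverage. The planned power check should therefore use the case count after the exclusion.
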